**Figure 1 Study Design**

Predecessor Studies	LONG TERM EXTENDED (LTE) STUDY					
	Predecessor EOT/ V1	V2	V3 - V14	V15	V16, V17	CCI
Week 0-48 (D5180C00007)	Week 52 Visit (D5180C00007)		Week 56-100	Week 104	Week 110, 116	CCI
Week 0-44 (D5180C00009)	Week 48 Visit (D5180C00009)	Week 52 for D5180C00009 only				
Treatment Phase	Screening/ Randomization	Treatment Phase		End of Treatment	Follow-up	CCI

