## 4 Study Design

### 4.1 Overall design

For an overview of the study design see [Figure 1](#), in Section [1.3](#). For details on treatments given during the study, see Section [6.1](#) Treatments Administered.

For details on what is included in the safety and efficacy endpoints, see Section [3](#) Objectives and Endpoints.

This is a multicentre, randomized, double-blind, placebo-controlled, parallel group, long-term extension study to evaluate the safety and tolerability of 210 mg Q4W SC of tezepelumab in adults and adolescents with severe uncontrolled asthma. Subjects who have continued to receive investigational product and have attended the EOT visit in one of the predecessor studies may be eligible to enroll into this study if they fulfil the inclusion/exclusion criteria.

Tezepelumab - D5180C00018

This study will be run at approximately 350 sites worldwide and will randomize approximately 975 subjects worldwide. All subjects will be re-randomized in this study to maintain the blinding. Subjects previously randomized to the 210 mg tezepelumab Q4W SC arm in either of the predecessor studies, will be assigned and remain on 210 mg tezepelumab Q4W SC dosing in the LTE study. Subjects randomized to placebo arm in the predecessor studies will be re-randomized in a 1:1 ratio to either 210 mg tezepelumab or placebo, both administered Q4W SC. Given the randomization scheme of subjects in the predecessor studies, this will give an overall subject distribution of 3:1 (tezepelumab:placebo).

Subjects who prematurely discontinue IP or do not attend the EOT visit in one of the predecessor studies will not be eligible to participate in the Long-Term Extension (LTE) study.

In order to provide sufficient time for subjects to consider participation in this study, and to ensure an uninterrupted dosing regimen, as subjects transition between the predecessor study and this study, subjects will be provided with the ICF at/after the visit at which they receive their last dose of IP in the predecessor study and will be asked to sign the ICF at Visit 1 of this study prior to any study-specific procedures being performed.

Section 6.5 (Table 6 and Table 7) provides a list of medication restrictions and prohibitions to be followed throughout conduct of the clinical trial. See inclusion criteria Section 5.1.

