### **On-Site Randomization, Treatment and Follow-up for subjects that rolled over from D5180C00007 or D5180C00009**

**Please NOTE:** If a subject is unable to attend an onsite EOT visit in NAVIGATOR or SOURCE due to the COVID-19 pandemic please refer to [Appendix H](#) for further guidance on roll over and participation into the DESTINATION study.

The study will consist of a screening/randomization visit which will be the same day as the End of Treatment (EOT) visit from the predecessor studies D5180C00007 (Week 52) or D5180C00009 (Week 48). The first dose of IP will be administered the same day. During the screening/randomization visit, subjects must undergo all assessments per [Table 1](#). Prior to randomization the subjects must meet all inclusion/exclusion criteria for LTE study. If a subject does not meet all inclusion criteria or meets any exclusion criteria as per [5.1](#) and section [5.2](#), the subject will be screen failed and would then complete the safety follow-up portion of the predecessor study. Further details are specified in section [5.4](#).

A treatment period duration of 52 weeks for subjects who previously completed study D5180C00007 or 56 weeks for subjects who previously completed the D5180C00009 will follow. The last dose of IP will be administered at Week 100. EOT visit will be conducted at Week 104. IP will not be administered at week 104. This is followed by a 12-week follow-up period which includes 2 follow-up visits (Visit 16 and Visit 17).

Tezepelumab - D5180C00018

Subjects who prematurely discontinue IP during the LTE study will be encouraged to undergo all study visits/procedures for the full treatment period. Further information is provided in section 7.1.1. Any new treatments that are initiated will be recorded in the electronic case report form (eCRF).

CCI

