## **6.4 Treatment compliance**

Any change from the dosing schedule or dose discontinuations should be recorded in the eCRF. The IP Storage Manager is responsible for managing the IP from receipt by the study site until the destruction or return of all unused IP. The date and time of all IP administrations, as well as any missed doses, should be recorded in the appropriate section of the eCRF.

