2.1.2 Treatment groups

There are 5 possible groupings across the predecessor and LTE studies as shown in Figure 2 below.

Figure 2 Treatment groupings

[figure not shown]

Note: Groups 2 and 5 reflect subjects in the predecessor studies who do not enrol in the LTE study.

The following treatment groups for analyses will be considered, where time from first dose is applicable for the safety analysis, and time from randomisation is applicable for the efficacy analysis:

Primary (based on the SAF and FAS analysis sets):

[figure not shown]
- Randomised Tezepelumab (Rand Teze): All subjects originally randomised to tezepelumab in the predecessor studies. Will include all data from first dose/randomisation in the predecessor studies to end of the LTE study. (A, B and C)
- Randomised Placebo (Rand Pbo): All subjects originally randomised to placebo in the predecessor studies. Will include all data from first dose/randomisation in predecessor studies up until switch to tezepelumab, and all data from first dose/randomisation in the predecessor studies to end of the LTE study for subjects randomised to placebo in the predecessor studies and the LTE study. (D, F, G and H)

Supportive (based on the SAF-LTE and FAS-LTE analysis sets):

[figure not shown]
- Tezepelumab Predecessor+Tezepelumab LTE (Teze+Teze): All subjects originally randomised to tezepelumab in the predecessor studies and re-randomised to tezepelumab in the LTE study. Will include all data from first dose/randomisation in the predecessor study to end of the LTE study for only subjects enrolled into the LTE study. (A and B)
- Placebo Predecessor+Placebo LTE (Pbo+Pbo): All subjects randomised to placebo in the predecessor studies, and later re-randomised to placebo in the LTE study. Will

include all data from first dose in predecessor studies until end of the LTE study for only subjects enrolled into the LTE study. (F and G)

[figure not shown]
Supportive (for exposure summaries and rare events based on the SAF analysis set):

[figure not shown]
• All Tezepelumab (All Teze): All subjects randomised to tezepelumab in the predecessor studies and subjects randomised to tezepelumab in the LTE study. It will include all data from time of first dose/randomisation to tezepelumab. (A, B, C and E)

Additional (for the assessment of durability of benefit based on the SAF-LTE and FAS-LTE analysis sets):

- Tezepelumab Predecessor+Tezepelumab LTE (Teze+Teze): as defined above

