- The most common AEs (defined as those occurring in ≥3% of subjects in either treatment group) by PT only for on-treatment period only

All AEs (by PT) will be summarised additionally by causality and maximum intensity. For summaries based on the number of subjects reporting at least one occurrence of the event, if a subject reports multiple occurrences within each PT, the maximum intensity will be taken as the highest recorded (the order being mild, moderate and severe) respectively.

In addition, each AESI category will be summarised by causality.

The AESI of injection site reactions will be further summarised for the on-treatment period by:

- Site of injection (arm, thigh, abdominal wall)
- Total number of doses administered (1, 2, ..., 26), irrespective of timing of the injection site reaction event.

Events confirmed by the independent adjudication committee (major adverse cardiac events (MACE) and malignancies) will be summarised by treatment. All events submitted for adjudication will also be listed for the SAF-LTE analysis set.

Further AE summaries will also be provided for overall summary of AEs, AEs by SOC and PT, SAEs, DAEs and each AESI category separately, for the on-treatment data. These summaries will be provided overall for the SAF (All Tezepelumab) analysis set.

Furthermore, AESI summaries described above will be repeated using exposure adjusted occurrence rates defined in Section 3.2.2.

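### The injection site reaction table groups subjects by their eventual total number of doses, so it cannot show whether risk changes with dose number

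*SAP*

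**What the plan says.** SAP section 4.5.1 announces two extra cuts of this adverse event of special interest: "The AESI of injection site reactions will be further summarised for the on-treatment period by" site of injection and "Total number of doses administered (1, 2, ..., 26), irrespective of timing of the injection site reaction event". The same section requires each adverse event summary to give the number and percentage of subjects with an event and the exposure adjusted incidence rate per 100 subject-years. It also repeats the AESI summaries as exposure adjusted occurrence rates. Table 10 in SAP Appendix 8.4 plans the injection site reaction summaries for the SAF groups overall, and for the SAF-LTE groups overall and by predecessor and LTE period (by period only for placebo-to-tezepelumab subjects).

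For Randomised Placebo, SAP section 2.1.2 limits the data of subjects who cross over: "Will include all data from first dose/randomisation in predecessor studies up until switch to tezepelumab". Protocol section 7.1 lists subject decision, and an adverse event that jeopardises safety, among the reasons for stopping investigational product (IP).

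On data capture, Protocol section 6.4 states: "The date and time of all IP administrations, as well as any missed doses, should be recorded in the appropriate section of the eCRF". Protocol section 8.3.4 collects the start date of each adverse event. No unredacted part of the SAP plans a summary of injection site reactions by dose number at onset.

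**The concern.** With up to 26 injections per subject, a reader of a table of reactions against dose count will ask whether the risk is highest at the first injections or grows with repetition. The planned row variable is the final dose count, which is not known when the reaction happens.

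- A subject who reacts at dose 1 and then completes is counted in the 26-dose row.
- A subject who stops because of a reaction is counted in a low row.

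Rows therefore differ in how many chances there were to react and in whether a reaction ended dosing. Neither difference is a change in risk per injection. What is at stake is a misreading of a protocol-defined AESI in a study whose primary objective is long-term safety.

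**Working it through.** **1. The plan's own figure.** Dosing is every 4 weeks ("will be assigned and remain on 210 mg tezepelumab Q4W SC dosing in the LTE study"). Protocol Figure 1 gives predecessor dosing as "Week 0-48 (D5180C00007") and "Week 0-44 (D5180C00009"), and Protocol section 4.1 states "The last dose of IP will be administered at Week 100".
- D5180C00007: Weeks 0 to 48 give 48/4 + 1 = 13 doses. Weeks 52 to 100 give another 13. Total 26.
- D5180C00009: Weeks 0 to 44 give 44/4 + 1 = 12 doses. Weeks 48 to 100 give 14. Total 26.

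The SAP's maximum of 26 is reproduced.

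**2. Model.** The documents give no reaction or reaction-driven stopping rates, so these inputs are assumptions:
- constant reaction risk per injection, h = 0.003;
- background stopping after each dose, b = 0.006;
- probability q that a reaction leads to stopping, set to 0, 5% or 10%.

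Doses are 28 days apart with none missed, and the denominator in row k is the subjects whose total is k. The SAP does not state the row denominator.

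Share of subjects in row k with at least one reaction:
- k < 26: 1 − [(1−h)/(1−hq)]^(k−1) × (1−h)b / {(1−h)b + h[1−(1−b)(1−q)]}
- k = 26: 1 − [(1−h)/(1−hq)]^25 × (1−h)
- with q = 0 both reduce to 1 − (1−h)^k.

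Exposure per SAP section 3.2.1 (last dose plus 33 days, minus first dose, plus 1) is 28(k−1) + 34 days. That is 34, 370 and 734 days for rows 1, 13 and 26, or 0.0931, 1.0130 and 2.0096 years.

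**3. Results when the true risk is constant.**

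| q | Measure | Row 1 | Row 13 | Row 26 |
|---|---|---|---|---|
| 0 | % with a reaction | 0.30 | 3.83 | 7.51 |
| 0 | per 100 subject-years | 3.2 | 3.8 | 3.7 |
| 5% | % with a reaction | 2.72 | 5.99 | 7.17 |
| 5% | per 100 subject-years | 29 | 5.9 | 3.6 |
| 10% | % with a reaction | 5.02 | 8.05 | 6.82 |
| 10% | per 100 subject-years | 54 | 8.0 | 3.4 |

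Example for row 1, q = 10%: the chance of stopping after a reaction is 1 − 0.994 × 0.9 = 0.1054. The share is 0.003 × 0.1054 / (0.003 × 0.1054 + 0.997 × 0.006) = 5.02%, and 0.0502/0.0931 gives 54 per 100 subject-years.

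**4. A different truth with a similar table.** Suppose all risk is at the first injection (5%, then none) and q = 0. Every row shows 5%. The rates are 0.05/0.0931, 0.05/1.0130 and 0.05/2.0096, that is 54, 4.9 and 2.5 per 100 subject-years. This is close to the 54, 8.0 and 3.4 produced by constant risk with q = 10%. The planned statistics can hardly separate the two situations. Tabulating by dose at onset does: it returns 0.3% at every dose in the first case, and 5% at dose 1 then 0% in the second.

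**5. What ends up in rows 12 and 13 of the SAF table.** Protocol section 9.2 assumes that 90% complete the predecessor study and 90% of those continue.
- Entering the LTE: 0.90 × 0.90 = 81%.
- Completing but not entering: 0.90 × 0.10 = 9%.
- Randomised Placebo subjects cut at the switch: 81%/2 = 40.5%.

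With no missed doses, about 9% of Randomised Tezepelumab and 9 + 40.5 = 49.5% of Randomised Placebo have totals of 13 (D5180C00007) or 12 (D5180C00009) for these reasons alone. Subjects who stopped early at that count are added to them.

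**The case against.** The strongest reply is that the SAP already requires exposure adjusted rates, so the rise in percentages (7.51/0.30, about 25-fold) would mislead only someone who ignored the rate columns. That is right when reactions do not cause stopping: the rates are then flat. It fails once a small fraction do, and the SAP does not state that dosing ends independently of reactions. The 10% value is an assumption, and injection site reaction is not a listed study-specific discontinuation criterion. It implies at most about 13 × 0.003 × 0.10 = 0.4% of subjects stopping for this reason over 13 doses. Protocol section 2.2 reports 1.2% of Phase 2b tezepelumab subjects stopping IP for any adverse event, so the value is not extreme.

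It is also fair that the SAP labels the cut as ignoring timing, makes no claim about risk by dose number, and tests no hypotheses. Some timing information exists elsewhere: the predecessor/LTE split and the dated listings. It is coarse, however, and adverse events are listed only for SAF-LTE, which leaves out anyone who stopped before an LTE dose.

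Three stronger readings are tempting but not supported.
- *The placebo comparison fails in rows 14 to 26.* Those rows hold only LTE entrants on unchanged treatment in both groups. The mismatch lies at rows 12 and 13, and the SAF-LTE comparison of continuous tezepelumab with continuous placebo has no switch cut.
- *Nearly everyone falls in the 26-dose row.* Under the plan's own roll-over assumptions, at most 81% of Randomised Tezepelumab and 40.5% of Randomised Placebo can pass 13 or 12 doses.
- *The overall safety comparison of injection site reactions is biased.* Overall incidence, occurrence rates and causality summaries do not use the total-dose row.

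**Conclusion.** The point holds for this one descriptive sub-table. Because the row is fixed after the event and can be caused by it, neither the percentages nor the planned rates show how risk moves with dose number. Under constant risk the rates are flat without reaction-driven stopping and fall about 16-fold from row 1 to row 26 (54/3.4) with 10% reaction-driven stopping. The direction rests on the structure of the table; the size rests on the assumed values of h, b and q.

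These are expected values. Row 1 would hold about 0.6% of subjects (0.003 × 0.1054 + 0.997 × 0.006), so an observed low row would also be very noisy. The rows at 12 and 13 doses additionally mix early stoppers, completers who did not enter the LTE and, for Randomised Placebo only, subjects cut at the switch. Conclusions on overall injection site reaction rates by treatment group are untouched.

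**What to change.** In SAP section 4.5.1, tabulate injection site reactions by the ordinal number of the most recent dose before onset (1, 2, ..., 26). Use as denominator the subjects in that treatment group who received that dose. State how reactions with partial onset dates are assigned, since SAP section 3.2.2 places them in the on-treatment period but not at a dose. Because only the onset date is collected, also state that onset on a dosing day counts towards that day's dose.

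The total-dose table can be replaced, or kept with a footnote saying that it does not show risk by dose number.

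The cost is one SAP sentence with its date rule and the programming of one table. Dose dates and adverse event start dates are already recorded, so no new data are needed.

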4.5.1.1 Subgroup analyses

The following AE summaries will also be provided by subgroups as defined in Section 3.1.8 for the on-treatment period for the SAF and SAF-LTE analysis sets for study D5180C000007 as predecessor only:

- SAEs
- DAEs

In addition, the overall summary of AEs as well as the summary of AEs by SOC and PT for the on-treatment period will also be provided by subgroups for the SAF analysis set and study D5180C00007 only.

4.5.2 Laboratory data

All continuous laboratory variables will be summarised by absolute value at each visit by treatment group, together with the corresponding changes from baseline. These summaries will be produced for the on-study period, as defined in Section 3.1.5, for the SAF analysis set for the Randomised Tezepelumab and Randomised Placebo treatment groups, as well as for the SAF-LTE analysis set for the Tezepelumab Predecessor+Tezepelumab LTE and Placebo Predecessor+Placebo LTE treatment groups. Summaries for the SAF-LTE analysis set for the Placebo Predecessor+Tezepelumab LTE treatment group will also be provided. The summary statistics presented will be the minimum, 1st quartile, median, 3rd quartile, maximum, mean and SD.

Central laboratory normal reference ranges will be used for the identification of individual clinically important abnormalities. A shift table will be produced for each laboratory variable to display low, normal and high. The shift tables will present baseline and maximum/minimum/last post-baseline values for each variable.

Shift plots showing each individual subject's laboratory value at baseline and at maximum/minimum/last value post-baseline will be produced for each continuous laboratory variable. If any laboratory variables show any unusual features (high or low values or a general shift in the data points) at other time points, then shift plots of these data may be produced. The diagonal line of no change, and horizontal and vertical reference lines indicating the limits of the normal reference ranges, will also be displayed on the shift plots.

Both shift tables and shift plots will be produced using all data for the on-treatment period, as defined Section 3.1.5, for the SAF analysis set for the Randomised Tezepelumab and Randomised Placebo treatment groups, as well as for the SAF-LTE analysis set for the Tezepelumab Predecessor+Tezepelumab LTE and Placebo Predecessor+Placebo LTE treatment groups.

The frequencies of clinically noteworthy values (using normal reference ranges) occurring during the study will also be given.

In order to identify potential Hy's Law cases, maximum post-baseline TBL will be plotted separately against both maximum post-baseline ALT and AST, expressed as multiples of ULN. These plots will be produced on a log scale, with reference lines included at 2xULN for TBL, and at 3xULN for both ALT and AST. These plots will be produced using all data for the on-study period, for the SAF analysis set for the Randomised Tezepelumab and Randomised Placebo treatment groups, as well as for the SAF-LTE analysis set for the Tezepelumab Predecessor+Tezepelumab LTE and Placebo Predecessor+Placebo LTE treatment groups. The plots will also be produced separately for the predecessor period and LTE period for the SAF and SAF-LTE analysis sets, where the SAF-LTE analysis set will also include the Placebo Predecessor+Tezepelumab LTE treatment group.

For all subjects who meet the biochemical criteria for Hy's Law (potential Hy's Law cases), the relevant laboratory variables will be tabulated showing all visits for these subjects.

For urinalysis data, a shift table will be generated to present changes from baseline to maximum/last value post-baseline. All data for the on-treatment period will be used and will be presented for the SAF analysis set for the Randomised Tezepelumab and Randomised Placebo treatment groups, as well as for the SAF-LTE analysis set for the Tezepelumab Predecessor+Tezepelumab LTE and Placebo Predecessor+Placebo LTE treatment groups.

All summaries and figures will report laboratory data in SI units. Any data outside the central laboratory normal reference ranges will be explicitly noted on the listings that are produced for haematology, chemistry and urinalysis parameters for the SAF-LTE analysis set.

4.5.3 Vital signs

All vital signs variables will be summarised by absolute value at each visit by treatment group, together with the corresponding changes from baseline. This will also include weight, BMI and height (for study D5180C00007 adolescents only). These summaries will be produced for the on-study period, as defined in Section 3.1.5, for the SAF analysis set for the Randomised Tezepelumab and Randomised Placebo treatment groups, as well as for the SAF-LTE analysis set for the Tezepelumab Predecessor+Tezepelumab LTE and Placebo Predecessor+Placebo LTE treatment groups. Summaries for the SAF-LTE analysis set for the Placebo Predecessor+Tezepelumab LTE treatment group will also be provided. The summary statistics presented will be the minimum, 1st quartile, median, 3rd quartile, maximum, mean and SD.

AZ-defined reference ranges (see Section 3.2.5) will be used for the identification of individual abnormalities. A shift table will be produced for each vital sign variable to display low, normal and high values. The shift tables will present baseline and maximum/minimum/last post-baseline values for each variable.

Shift plots showing each individual subject's vital signs value at baseline and at maximum/minimum/last value post-baseline will be produced for each continuous vital sign variable.

Both shift tables and shift plots will be produced using all data for the on-treatment period, as defined in Section 3.1.5, for the SAF analysis set for the Randomised Tezepelumab and Randomised Placebo treatment groups, as well as for the SAF-LTE analysis set for the Tezepelumab Predecessor+Tezepelumab LTE and Placebo Predecessor+Placebo LTE treatment groups.

Subjects who have changes from baseline outside the pre-defined AZ clinically important change criteria in Section 3.2.5 will be summarised. All data for the on-study period will be used, for the SAF analysis set for the Randomised Tezepelumab and Randomised Placebo treatment groups, as well as for the SAF-LTE analysis set for the Tezepelumab Predecessor+Tezepelumab LTE and Placebo Predecessor+Placebo LTE treatment groups. All recorded vital signs data will be listed.

4.5.4 12-lead ECG

The investigator's assessment of the 12-lead ECG (normal or abnormal) will be listed for all subjects, along with detailing whether any abnormalities were clinically significant or not for the SAF-LTE analysis set.

A shift table will be produced to display the investigator assessment of normal, abnormal – not clinically significant, abnormal – clinically significant and not done between baseline and end of treatment. For this purpose, borderline (also recorded on the eCRF) will be grouped with normal. This table will be produced for the SAF analysis set for the Randomised Tezepelumab and Randomised Placebo treatment groups, as well as for the SAF-LTE analysis set for the Tezepelumab Predecessor+Tezepelumab LTE and Placebo Predecessor+Placebo LTE treatment groups.

